A number of human physiological parameters correlate with mood and respond in the presence of stress, such as voice, skin conductance and pupil diameter. Capturing human voice or speech is generally less obtrusive than capturing other stress sensitive physiological signals, which require on-body sensing equipment and might also introduce safety concerns. As we focus on modeling and improving patient-caregiver relationships, we will build on sensing capability in acoustic events for monitoring patient and caregiver moods, stress and their vocal interactions. As the demands of caregiving for a person with ADRD escalate, many families struggle to maintain healthy relationships with each other, which directly leads to intensified stress on family caregivers. The stress on caregivers, in turn, exacerbates the disease and condition of ADRD patients. Therefore, detecting and modeling stress in caregivers, and providing them with just-in-time training and recommendations becomes crucial. It is a notorious difficult challenge to detect stress from voice, but our approach is to apply novel machine learning techniques that combine multi-instance learning and transfer learning. We have shown these techniques work well for detecting anxiety from voice [25], and propose to now apply this to stress detection.

The end-goals of our research are to provide real-time objective behavior monitoring to reduce in-home patient care cost and to improve the quality of interactions between persons with ADRD and their family caregivers. To achieve the goals, only passively recording what happened for posterior analysis and response is insufficient; real-time recommendation becomes necessary and beneficial to both patients and caregivers. For caregivers, this helps them improve their relation with patient, and may provide them with new insights of how their actions and reactions to their loved one with dementia can either calm or escalate a situation. Furthermore, from a system development perspective, patient's and caregiver's responses to the system's output, e.g., monitoring data, recommendations, become an invaluable source of supervision for us and the back-end automated system to further refine the deployed classifiers and control pipelines.

III. Procedures

A. Research Design

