There are two important research questions this study aims to address: 1) how to generate effective and accurate recommendations; and 2) how to adapt the recommendation generation according to patients' and caregivers' feedback. To the best of our knowledge, no existing in-home health monitoring system provides this capability, instead recommendations are developed in an ad-hoc manner and generated ahead of time and independently of the interaction dynamics. Due to the nature of dementia disease and the consideration of patient safety, we will *only study recommendations for caregivers*. But the technical solutions we examined here are general, and can be applied to other health recommendation scenarios. We should note that we are not replacing medical care; study participants (e.g., caregivers) will be provided information to seek help from their regular healthcare provider or emergency services as needed.

The proposed collaborative research will take place over four years and will follow the outlined timeline:

Year One: In the first year, focus will be on building the front-end monitoring architecture. In-suites sensing and monitoring components will be built and customized for collecting the

participants' vocal and psychological signals. Joint acoustic signal analysis and text mining algorithms will be explored. At this stage of single module development, offline dataset will be used for evaluation purpose. A study consultant, will also assist the study team in developing and pilot-testing a checklist to assess for fidelity of the educational training we deliver to caregiver participants.

Year Two: We will be working on system integration and unit test of the intergraded components in the system. In the meanwhile, from the second half of year two, we will start recruiting patients for our system deployment and evaluation purpose. The PI and research assistant will work with the recruitment clinic to consent and enroll the pilot patients, collect study data, and will be on-call to answer caregiver questions as they may arise. We set “5-7 patients enrolled per month” as our recruitment milestone, and thus it takes about 2 months to recruit 8-10 patients for phase 1 pilot study and about 4 months to recruit 25 patients for phase 2 system evaluation.

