2. TICS

During Visit 1, research personnel will prompt the family caregiver to establish an emergency plan. This plan is meant to reinforce use of previously established procedures or create procedures to be used in the event of an emergency. Research personnel will stress that the study equipment is not monitored and is not capable of contacting emergency services and should not be used for such activity. Examples of an emergency plan could include, but are not limited to, notifying a healthcare provider, calling 911, or calling another family member. Caregivers will be reminded periodically to follow the procedures of their emergency plan in the event of any emergency.

We anticipate Visit 1 will take between 90-135 minutes.

Between visits 1 and 2, participants will complete a short survey about their experience deploying the study equipment in their home. The questionnaire will take about five to ten minutes to complete.

Visit 2: Upon completion of the first two weeks to one month of baseline data collection, the trained Graduate Research Assistant will visit the study participants in their homes or set up a

virtual meeting via Zoom or telephone to educate the participants regarding the text messages they will be receiving from the study team when stressful situations are identified. The Graduate Research Assistant will also train caregivers on how to perform mindfulness-based activities. A standardized training guide will be used for all participants by the trained GRAs. During the visit, a principal investigator (PI) may monitor whether the stress management education is delivered as intended (i.e., intervention fidelity check) with no recordings. Retraining of GRAs may be performed based upon the results of fidelity checks. Caregivers will be asked to select personal preferences for messages and helpful reminders they will receive in the text messages that would prompt their understanding of the text messages received from a pre-set list of choices. Additionally, family caregivers will be taught to respond to the daily and weekly feedback surveys regarding their use of the text messages.

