Acoustic monitoring and text message recommendations will occur until study end. Trained GRAs will communicate with the family caregiver regarding any difficulties they are encountering with the acoustic monitoring and/or the text message recommendations they are receiving. We will send a text message within an hour after each recommendation is sent to a caregiver for the caregiver to tell us if he/she implemented the recommendation (yes or no) and to provide feedback on how helpful the recommendation was (not helpful at all – very helpful, using a 1-5 star rating). We will send morning text messages that contain a reminder for caregivers to follow their emergency plan in the event of any emergency, a prompt for self-reflection and setting a self-care goal, and encouraging words. We will send evening text messages to follow-up on their self-care goal and inquire about any recommendations that did not receive a response during the day. Additionally, we will text caregivers weekly and will ask them to rate the overall helpfulness of the recommendations (1-5 stars, as above). At each one month interval, participants will receive \$50 each, or \$100 per dyad, for their time and attention to the study protocol.

We anticipate Visit 2 will take 60 minutes.

Visit 3: The Graduate Research Assistant will visit the caregiver in his/her home or set up a virtual meeting via Zoom or telephone approximately one month after the recommendation system is initiated. Visit 3 will allow the research personnel to reinforce study training—including use of the smartphone, how to respond to text messages, and mindfulness techniques—and troubleshoot any issues that the caregiver may be experiencing.

We anticipate Visit 3 to take 30-45 minutes.

Visit 4: At the completion of the study, a trained GRA will visit the participant's home to collect the end of study measures, pay participants, and collect all study equipment. Additionally, interviews with participants regarding their feedback of the study procedures will be conducted and we will collect feedback via Smart Phones regarding the recommendations and their usability and acceptability. The interview that occurs during the course of the study will be video or audio recorded via Zoom and transcribed verbatim. The interview will take approximately 60 to 90 minutes. During the interview, all the recordings will be saved and retained in REDCap

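### Caregiver feedback follows only texts already sent and never asks whether a detection was right, so it cannot give the detector's in-home sensitivity or positive predictive value

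*Protocol*

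**What the plan says.** The first research question, in section III.D (Detailed study procedures), is "how to generate effective and accurate recommendations"; the second is how to adapt recommendations to feedback. Section III.E (Internal Validity) says that a recommendation goes out when the system detects an emotional reaction while the two people are together.

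The feedback channels are set out under Visit 2 in section III.D:

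- **After each text.** "We will send a text message within an hour after each recommendation is sent to a caregiver", asking "if he/she implemented the recommendation (yes or no") and inviting the caregiver to "provide feedback on how helpful the recommendation was" on a 1 to 5 star scale.
- **Evening text.** It follows up the self-care goal and will "inquire about any recommendations that did not receive a response during the day".
- **Weekly text.** Caregivers "rate the overall helpfulness of the recommendations".
- **Training.** Caregivers are taught to answer "daily and weekly feedback surveys regarding their use of the text messages".

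Section II (Background and Rationale) says that responses to the system's output, with monitoring data and recommendations as examples, "become an invaluable source of supervision for us and the back-end automated system to further refine the deployed classifiers".

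Section III.E then judges effectiveness partly by whether negative interactions, as recorded by the monitoring system, become less frequent, less intense and quicker to settle. The self-report scales are the other strand. Section III.A states that there is one group and no control.

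**The concern.** A detector makes two kinds of error: it fires when nothing tense is happening, and it stays silent when something is. Feedback triggered by a firing says nothing about the second kind. Here it does not settle the first kind either, because a low star rating may mean poor advice at a truly tense moment.

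Two things are at stake. The accuracy part of the first research question cannot be answered in the home from this feedback, and a detector refined on it is given no examples of what it missed. In addition, the detector is also an outcome instrument. Text feedback begins only after baseline, so refinement based on it falls in the second of the two periods being compared. If refinement changes sensitivity, the recorded frequency changes even when the household has not, and no concurrent control group would reveal this.

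**Working it through.** The protocol states no sensitivity, predictive value or event rate, so there is no figure of its own to reproduce. The check has three steps.

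**1. What each channel can label**

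| Channel | Depends on a text having been sent? | Asks whether the moment was tense? | Asks about moments without a text? |
|---|---|---|---|
| Message within an hour | Yes | No | No |
| Evening text, recommendation part | Yes | No | No |
| Evening text, self-care goal | No | No | No |
| Weekly rating | Yes | No | No |

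**2. What can be identified from such feedback**

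Let TP be correct detections, FP false alarms and FN missed events.

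- Sensitivity = TP / (TP + FN).
- Positive predictive value (PPV) = TP / (TP + FP).

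Assume, for illustration, 100 texts of which 80 came at truly tense moments. PPV = 80/100 = 0.80 whatever was missed. Sensitivity then depends wholly on the unseen FN:

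| Missed events (assumed) | Sensitivity |
|---|---|
| 0 | 80/80 = 1.00 |
| 20 | 80/100 = 0.80 |
| 80 | 80/160 = 0.50 |
| 320 | 80/400 = 0.20 |

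The feedback would be the same in all four rows. The split of 80 and 20 would also be unknown, because no item asks for it, so PPV is not observed either.

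**3. Effect on the frequency outcome**

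Recorded frequency = true frequency × sensitivity + false alarms. Assume 3 true events a day in both periods, so that nothing has really changed.

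| Sensitivity, baseline to later period | No false alarms | One false alarm a day (assumed) |
|---|---|---|
| 0.80 to 0.60 | 2.4 to 1.8: fall of 0.6/2.4 = 25% | 3.4 to 2.8: fall of 0.6/3.4 = 17.6% |
| 0.80 to 0.70 | 2.4 to 2.1: fall of 0.3/2.4 = 12.5% | 3.4 to 3.1: fall of 0.3/3.4 = 8.8% |
| 0.80 to 0.80 | No change | No change |

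For a given drop in sensitivity, the column without false alarms shows the largest distortion. A rise in sensitivity would act in the opposite direction and could hide a real benefit.

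**The case against.** A reader might infer that missed events can never be labelled, that sensitivity is unknowable, or that the classifiers learn only from their own detections. The protocol does not support this. Acoustic data are sent to the analysing university for analysis and storage (Planned procedures to protect against or minimize potential risks). Up to a month is recorded before any text goes out (Visit 1). Labelled instances are shared through transfer learning (section III.A), and an offline dataset serves the Year One module evaluation. Year Three brings an expert clinical panel and a review of monitored data and predictions. Section II does not say that replies to texts are the only supervision. Misses could also surface informally at the weekly check-ins, at Visit 3 or in the closing interviews. All of this stands, but none of it is described as annotating missed events in participants' homes.

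A reader might also infer that the ratings at least teach the detector to drop false alarms. They do not label false alarms, for the reason given above. They suit the second research question better than the first.

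Three further objections stand in part:

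- The self-report scales do not depend on the detector, so effectiveness does not rest on acoustic frequency alone.
- Scoring all audio with one frozen classifier is an analysis choice that a SAP, not shown here, could already hold. The questions put to caregivers are different: no later analysis can recover an answer that was never requested.
- Asking only about missed events would not yield sensitivity, because detections would remain unverified. Microphones are also expected only in the kitchen or dining area and the living room, and a tense moment elsewhere is not a detector miss.

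**Conclusion.** The point holds in a limited form. As planned, caregiver feedback can estimate neither the sensitivity nor the positive predictive value of the detector in the home, and refinement based on that feedback lacks labels for missed events. Whether the acoustic frequency outcome is biased depends on whether sensitivity changes between periods. Under the assumed 3 events a day and a drop from 0.80 to 0.60, the spurious fall is 25% without false alarms and about 18% with one a day. These inputs illustrate the mechanism and do not predict its size. Constant sensitivity would largely cancel from a within-dyad comparison. The protocol gives no evidence that sensitivity will drift, only no means in this feedback of detecting it. For a study whose main purpose is feasibility and testing of the model, this is an inexpensive improvement and does not invalidate the design.

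**What to change.** 1. Add one item to the message sent within an hour: was this in fact a tense moment?
2. Add one item to the existing evening text: how many tense interactions today brought no message, roughly when, and in which room? Events out of microphone range should neither count as detector misses nor serve as training labels.
3. For the baseline versus recommendation-period comparison of frequency, score all stored audio with one fixed classifier version. This assumes that the retained audio can be rescored. It removes drift caused by refinement, but not drift from other causes.
4. Report caregiver-based sensitivity (confirmed detections divided by confirmed detections plus in-range misses) and positive predictive value (confirmed detections divided by detections with an answer) as approximate, next to the acoustic frequency.

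If a daily count is also wanted during baseline, word it as all tense interactions, because no texts are sent then. Match it by time to the system's silent detections, and acknowledge that self-monitoring may itself affect the baseline.

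The cost is two short items in texts already scheduled, on phones handed over at Visit 1, plus one rescoring run. The drawbacks are a small added burden, same-day recall error and possible reactivity to being asked.

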The research design used in this project is a single-group, longitudinal design. All study participants will receive the interventions. Therefore, randomization is not occurring in this project and there is no control group.

This project focuses on building a behavior monitoring and recommendation system for in-home dementia patient care. In the front-end, a flexible sensing and communication platform will support the proposed monitoring, analytics, and recommendation tasks. In the back-end, we focus on multi-modal behavior monitoring with a special emphasis on patient and caregiver vocal events, and the behavior dynamics between them. In particular we focus on detecting mood and stress in a personalized and real-time manner.

To conquer sparsity issue in statistical model training and enable rapid deployment of analytical models, we will develop solutions based on transfer learning [22, 23, 6], such that the labeled instances and learned models can be shared across patients and monitoring scenarios. This further facilitates scalable deployment of our proposed in-home monitoring system.

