The **second** category are reminders to practice breathing awareness, which has a long history in the treatment of anxiety and stress, and is an effective and brief strategy to reduce physiological and emotional arousal both in non-clinical and clinical populations [34,35]. The GRA will go over this strategy with the caregiver by explaining the rationale behind this technique using exercises from the UCLA Mindful Awareness research center (see <http://marc.ucla.edu/mindful-meditations>) and then will practice the breathing skill with the caregiver until they have a good sense of how to do it.

The **third** category of reminders would be to engage in a brief mindfulness exercise that focuses on non-judgment and acceptance. Mindfulness strategies have been shown to reduce stress in caregiver populations [19,27] and more general studies have indicated that mindfulness reduces emotional reactivity and improves communication [19, 16, 27, 17]. Additionally, two RCTs indicate that brief psychoeducation on mindfulness and self-guided practice using online exercises significantly reduce depression and anxiety [30, 29], and a very brief intervention involving training in mindfulness and ecological momentary assessment strategies, which is similar to this project's methodology, significantly increased mindfulness skills [24]. In particular, awareness and acceptance strategies have been shown to be particularly effective in reducing anxiety and stress [19, 30]. The GRA will explain the rationale for this exercise and demonstrate it using transcripts from the UCLA Mindful Awareness research center. Mindfulness has been shown to be an effective technique in reducing emotional dysregulation in dyadic conflict [17]. They will again receive training from the GRA on this exercise and will be referred to the UCLA Mindful Awareness Center website to practice these exercise (or give an audio CD to them if they do not have access to the internet). We will recommend that they practice it daily as much as possible.

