Importance of the Knowledge to Be Gained. There may be immediate benefit to the subjects participating in the study, although we do not guarantee this, as family caregivers will be given specific knowledge and helpful reminders to mitigate potentially problematic behaviors regarding care of their loved one with ADRD. If successful, the knowledge gained will be important because of its substantial potential to enhance the treatment of difficult to manage, prevalent, and burdensome care problems of persons with ADRD, increasing their quality of life, reducing caregiver burden, delaying or reducing institutionalization, and decreasing the costs of caring for persons with AD in the future.

E. Internal Validity

The purpose of this study is primarily to establish feasibility and test the model. If we can establish that our system reduces emotional reactivity and that patient and caregiver self-reported and observed outcomes improve over time compared to an individualized baseline period, we will have established justification for a more comprehensive design that will more fully test this system against a credible alternative.

Thus, the caregivers will fill out the measures provided to them and then their interactions with the patients will be monitored for a month to establish a baseline of functioning. We will assess levels of reactivity during caregiver-patient interactions and the time it takes for them to return to their own baseline. At the end of the one-month assessment period, the caregiver will be brought in for training on the recommendations, after which they will receive recommendations when the system detects emotional reactions when the caregiver and patient are with each other. The recommendations will be personalized over time. Effectiveness of the recommendations will be assessed by examining whether the recommendations reduce the frequency and intensity of the negative patient-caregiver interactions and the time required for reactivity to return to baseline in real time, as assessed by information recorded by the monitoring system. Effectiveness also will be assessed by monitoring change in the self-report measures during the baseline period compared to the period in which the caregiver is receiving the recommendations.

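### The protocol plans to credit the before-after change to the triggered recommendations, but the design shows only the joint change under the whole package plus time

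*Protocol*

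**What the plan says.** Protocol section III.A states that "randomization is not occurring in this project and there is no control group".

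The content of the intervention is spread over several places:

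- **Training.** Section III.D, Visit 2, after the baseline recording: "The Graduate Research Assistant will also train caregivers on how to perform mindfulness-based activities".
- **Daily practice.** Section III.A, third category of reminders: "We will recommend that they practice it daily as much as possible". This advice does not depend on any text being triggered.
- **Morning texts.** Described under Visit 2. Besides an emergency-plan reminder they carry "a prompt for self-reflection and setting a self-care goal, and encouraging words".
- **Evening texts.** Also under Visit 2: "We will send evening text messages to follow-up on their self-care goal".
- **Triggered recommendations.** Section III.E has the caregiver trained, "after which they will receive recommendations when the system detects emotional reactions". Under Visit 2 these run to the end of the study.
- **Visit 1 content.** Section III.A, fourth category, places the information on unmet needs and the choice of pleasant activities at the first study visit.

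Section III.E then sets the effectiveness question: "Effectiveness of the recommendations will be assessed by examining whether the recommendations reduce the frequency and intensity of the negative patient-caregiver interactions". The same sentence adds the time reactivity takes to settle, measured by the monitoring system. A second criterion compares self-report measures between the baseline and recommendation periods. The same section ties the justification for a later study to a causal result: "If we can establish that our system reduces emotional reactivity".

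**The concern.** The wording in III.E names one component as the cause of the change. The comparison behind it contrasts a period with almost none of the intervention with a period that contains all of it. A fall in negative interactions, or a better self-report score, could come from the training, the practice, the daily texts, the triggered recommendations, the passage of time, or any mix of these.

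This matters because section III.D presents recommendations that respond to the interaction as what existing systems lack. If training or daily encouragement produced the improvement, III.E as worded would credit it to the sensing-triggered texts. The reader of the results, and the designers of the next study, would then have the wrong idea of which component carries the effect.

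The protocol's own evidence makes the rival explanation credible. The third-category text in III.A cites two randomised trials in which brief mindfulness education with self-guided practice lowered depression and anxiety. Depression and anxiety are two of the three DASS scales used here. On that reasoning, DASS scores could improve even if no triggered text had any effect.

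**Working it through.** The protocol gives no effect size, standard deviation, significance level or power for this question, so there is no stated figure to reproduce. The check concerns what the design can identify.

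**Step 1: write down the contrast.** Let the post-baseline terms be training T, practice P, morning and evening texts D, triggered recommendations R, and time τ (trend and regression to the mean). With baseline mean μ₀ and post-baseline mean μ₁:

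μ₁ − μ₀ = T + P + D + R + τ

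This is one equation in five unknowns.

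**Step 2: check the rank.** Code a baseline row as (1,0,0,0,0,0) and a post-baseline row as (1,1,1,1,1,1), with columns for intercept, T, P, D, R and τ. The matrix has rank 2 for 6 parameters. Adding the Visit 1 content as a term present in both monitored periods gives rank 2 for 7. Only the baseline mean and the sum of the post-baseline terms can be estimated. More dyads repeat the same two rows and do not raise the rank.

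**Step 3: look for a feature that would separate the terms.** The protocol describes no period with training alone, no withheld or randomised prompts, and no withdrawal of the recommendations. Detected episodes without a prompt belong to the baseline, before training, so prompted against unprompted largely repeats before against after training.

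**Step 4: consider the remaining terms.** Caregivers enter only if they score above 3 on the RMBPC (III.B), which is also a Visit 1 survey. Selection on a high score makes some later fall likely without any intervention, on that scale and on measures correlated with it. This is part of τ.

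**Step 5: illustrate the size.** Assume R = 0 and that the other terms shift the mean by d standard deviations of the within-dyad change. For a paired t-test at two-sided 0.05 (assumed), the probability of significant improvement is the upper tail of a noncentral t with n − 1 degrees of freedom and noncentrality d√n. The target in III.B is n = 30. The lower value, n = 25, is what 50 enrolled dyads leave at 50% attrition: 50 × 0.5 = 25.

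| Assumed d | n = 30: d√n | n = 30: probability | n = 25: d√n | n = 25: probability |
|---|---|---|---|---|
| 0 | 0 | 0.025 | 0 | 0.025 |
| 0.2 | 1.10 | 0.184 | 1.00 | 0.159 |
| 0.3 | 1.64 | 0.355 | 1.50 | 0.302 |
| 0.5 | 2.74 | 0.754 | 2.50 | 0.670 |

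The values of d are assumptions. The table shows how often a conclusion that the recommendations work would be drawn when they do nothing.

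**The case against.** **The limitation is disclosed.** The protocol states that there is one group and no control, that feasibility is the primary purpose, and that a later study will compare the system with an alternative. This stands and lowers the severity. It concedes the missing comparator for the system as a whole. It does not concede that the triggered texts cannot be told apart from the training and daily texts given in the same period.

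**The terms may be shorthand.** The interview plan later in III.E treats training and text messages as examples of what the recommendations cover, and the system can fairly mean the whole package. This stands in part. But III.E also separates training from the recommendations that follow it, and Visit 2 lists the daily texts apart from the triggered ones. If shorthand was meant, the rewording makes that plain.

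**Episode-level data exist.** Recovery is measured in real time, caregivers report whether they acted on each recommendation, and practice is logged. The two-period matrix leaves out this variation, and how to model it may belong in an analysis plan that is not shown. These data can support exploratory work. They do not isolate the recommendations, because acting on one is the caregiver's choice and no unprompted comparison episodes are planned after training.

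**Stronger readings that a reader might infer.** One is that every component switches on at a single visit. The documents do not support this: part of the fourth category is given at Visit 1, and the start of the morning and evening texts is implied only by their place under Visit 2. Another is that the recommendations' share must lie between 0% and 100%. That is not a valid bound, since components or time may act in opposite directions and put the share outside it. The supported statement is that the share is not identified.

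**Conclusion.** The point holds as a mismatch between the conclusion planned in III.E and what the design can show. A before-after comparison here estimates the joint change under training, practice, daily texts and triggered recommendations, together with time and regression to the mean. It does not estimate the part due to the triggered recommendations. Even with the system read as the whole package, a causal statement lacks a comparator.

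The identification result needs only the single group and the shared post-baseline period, with the daily texts starting where the protocol describes them. If those texts began earlier, training, practice and triggered recommendations would still coincide. The probabilities in the table depend on assumed shifts and an assumed paired test, and show scale only.

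Severity is minor. The protocol calls itself primarily a feasibility study and leaves the comparative test to later, so the planned next step already includes a comparison. The finding does not count against the study's feasibility aims or its choice of a single-group design.

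**What to change.** In section III.E:

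- State the effectiveness question as before-after change under the whole package, and name its parts: training, practice, daily texts and triggered recommendations. Make no causal attribution to the triggered recommendations or to the system.
- Keep the frequency and intensity of negative interactions, and real-time recovery, as outcomes at package level.
- Report per-recommendation implementation and helpfulness, and any within-dyad analysis of episodes, as descriptive or exploratory.
- Note that some fourth-category content is given at Visit 1, and say when the morning and evening texts begin, so that the reader knows what the baseline contains.

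The cost is a few sentences. No visit, procedure, measure or sample size changes. The downside is a more modest claim.
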